Primary: Disease control rate at 24 weeks after initiation of tamoxifen (since day 1 cycle 1), defined by absence of radiological progression in conventional imaging

examinations by RECIST 1.1 (Appendix I). Isolated increase of biomarker (chromogranin A) or specific hormone will not be considered progression.

Secondary:

(1) Progression-free survival, defined by time from tamoxifen day 1 cycle 1 to death from any cause or radiological progression by RECIST 1.1, whichever occurs first. Patients alive and without progression at the time of study analysis will be censored for time-to-event analysis.

(2) Biochemical response will be defined by at least 30 percent drop in the marker (chromogranin and / or specific hormone) at any time of treatment in relation to pre-treatment value (s).

(3) Radiological response rate by RECIST criteria 1.1 during the study period.

(4) Disease control rate, defined by absence of radiological progression by RECIST 1.1 criteria, according to the intensity of expression by immunohistochemistry (IHC) of HR and also according to primary site (pancreas, gastrointestinal or lung) during the study period.

(5) Toxicities frequency: Adverse events of grades 2 or more by Common Adverse Event Toxicity Criteria (CTCAE) version 5.0 during the study period.

Exploratory:

(1) Evaluate possible variations in intensity and number of sites between PET-CT gallium-68 pre-treatment and 12 weeks after initiation of tamoxifen as a continuous variable for each capture lesion. Although this examination is part of the evaluation routine of NET, in this study we will evaluate differences in the intensity of uptake with tamoxifen.

(2) Evaluate the percentage of CTC positivity in NET, as well as average number of cells in case of positivity. To evaluate the presence of estrogen and progesterone receptors in CTC.

Methodology:

Study design:

A single-arm, unicentric, single-stage clinical study of tamoxifen for patients with well differentiated neuroendocrine tumors and radiological progression with positive (> 1 percent) HR (estrogen and / or progesterone) expression by IHC.

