Patients eligible for the clinical and radiological criteria and signing the Informed Consent Form (ICF) will have the biopsy material (tumor stored in paraffin) evaluated for IHC of HR. If the expression is positive, eligibility will be complete and patients will receive tamoxifen continuously until radiological progression by RECIST 1.1, unacceptable toxicity or withdrawal of consent. If the expression for HR is negative, the patient will be informed of their ineligibility for this study and will continue to be treated by the Clinical Oncology team without any detriment to their care.

Patients will be followed up by the study team for assessments of:

(1) Safety: first in 3 weeks after tamoxifen day 1 cycle 1, and then every 6 weeks from tamoxifen day 1 cycle 1 for anamnesis with active questioning of disease symptoms and possible adverse events, physical examination and routine laboratory routine (hemogram, biochemistry, liver and renal function);

(2) Efficacy: patients will perform imaging (chest, abdomen and pelvic tomography or abdominal and pelvic resonance imaging) at baseline or pre-treatment and every 12 weeks until progression or intolerance / exit from the study. The image response evaluations will be through RECIST 1.1. For evaluation of the biochemical response, patients will undergo hormonal dosing with serum chromogranin A and specific hormones in cases of functioning NET (eg 5-HIAA dosing in 24-hour urine) at the baseline and every 12 weeks until progression (increased chromogranin and / or the functioning hormone will not be characterized as disease progression if imaging shows progression).

(3) Exploratory assessment: Patients will be assessed for somatostatin receptor expressiveness by the functional examination of PET-CT Gallium-68, which will be performed before treatment and at week 12. This evaluation, because it is exploratory, does not will be part of the definition of disease progression.

Also as an exploratory analysis, a blood sample will be collected to search for circulating tumor cells at the baseline visit (a collection only).

After a period of one year, the consultations laboratory and imaging examinations will be performed every 12 weeks until the disease progresses. Collection and evaluation times are summarized in the Table of Procedures (TABLE 1).

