The main adverse effects of tamoxifen are hot flushes, dry skin, nausea, vaginal discharge, fatigue and changes in the menstrual cycle. Rarely, but importantly may be associated with retinal changes, hepatotoxicity, hematological changes, thromboembolic phenomena and endometrial neoplasia. Given the teratogenic potential, women of childbearing potential should undertake contraceptive measures. Such medication should be contraindicated in cases of hypersensitivity to tamoxifen or any component of the formulation, concomitant use of coumarins and history of deep vein thrombosis or pulmonary embolism.

Administration

The treatment to be used will be tamoxifen 20mg VO once daily with a glass of water. In cases of vomiting occurring after 1 hour of taking or when a dose is missed, the patient will be instructed to skip this dose and not compensate for the next dose. Each cycle will be defined for 42 days (6 weeks).

Aderence:

The dispensation of tamoxifen will be made by the research pharmacy of the institution. Approximately 20 mg tamoxifen tablets will be given to each patient until the next return to the oncologist (see TABLE 1).

To assess adherence to treatment we will require patients to bring the blisters at each visit and at the time of discontinuation of treatment.

Dose reduction:

Dose interruption or reduction will be allowed in case of any toxicity of degree equal to or greater than 3 or intolerable grade 2 toxicity, as shown in the table below.

TABLE 3 - Dose adjustment according to toxicity

Study drug and dose	Tamoxifen 20mg orally once daily
Haematological or non-haematological toxicity grade \geq 3 or grade 2 intolerable.	Suspend therapy until recovery of the condition (with weekly evaluation by the investigator until the end of the recovery). When improvement of the picture (grade 1 toxicity), restart with tamoxifen 10mg tablet orally daily If there is no improvement in clinical status within 3 weeks (persisting with grade 3 or grade 2 intolerable toxicity) or patient does not tolerate the 10 mg / day dose, the patient will be excluded from the study for unacceptable toxicity.
Haematological or non-haematological toxicity <grade 2	No dose reduction will be performed for tolerable grade 1/2 toxicities.

Security Assessment

Baseline Assessment:

After signing the informed consent form, patients will be submitted to baseline evaluation to assess the patient's eligibility (see TABLE 1):

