For evaluation of efficacy, patients will perform imaging (chest tomography, abdomen and pelvis or abdominal and pelvic resonance) at baseline and every 12 weeks until progression or intolerance. Patients will also be evaluated for signs and symptoms that may be related to disease progression. Patients who present clinical progression at the investigator's judgment, but without radiological progression, may discontinue treatment with tamoxifen and continue imaging until progression; however, if new treatment is instituted, the last date of receipt of tamoxifen will be the date of censure in the analysis of progression-free survival.

Patients will also be evaluated for somatostatin receptor expressiveness through the functional examination of PET-CT Gallium-68, which will be performed before treatment and at week 12, in addition to biochemical response through the dosage of chromogranin A and / or specific hormone every 12 weeks, in conjunction with imaging (tomography and / or resonance). An interval of +/- 5 days will be

allowed for imaging and PET-CT Gallium-68 exams. Patients with suspected progression (eg worsening of symptoms) may perform images within less than 12 weeks to assess progression of disease, at the discretion of the investigator.

After documentation of progression or exit from the study for other reasons, patients will be followed up by the investigator or other oncologist from the Clinical Oncology team for symptom control, imaging monitoring and possible future therapies. The patient continues to be cared for at the AC Camargo Cancer Center, if desired.

Other concomitant medications

In general, concomitant medications and therapies deemed necessary for the intensive treatment and safety of the patient are permitted provided that their use is documented in the patient's records and in the appropriate clinical record. Tamoxifen may have drug interaction with coumarin anticoagulants (Marcoumar, Marevan, Coumadin) and those with some of the new anticoagulants (Pradaxa, Xarelto). These drugs should be avoided during the study (moderate contraindication). Concomitant administration of investigational medicinal products is not permitted. Administration of any other anticancer agents including chemotherapy, target therapy and biological agents is not permitted.

Statistical Considerations

Statistical plan

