Descriptive statistics will be used to report the results of categorical and continuous variables. The time-to-event variables will be reported in medians and Kaplan Meyer curves. The degrees of toxicity will be tabulated. The number of patients discontinuing treatment due to toxicity will be presented.

Efficacy and toxicity analyzes will be performed by intention to treat. Patients receiving at least one dose of tamoxifen will be evaluated for toxicity and efficacy.

Inferential analyzes of the primary outcome according to primary site and IHC HR expression intensity will be conducted to depend on the number of cases per subgroup; if possible, these analyzes will be performed with the chi-square test. The analyzes of intensity of uptake intensity to PET-CT gallium-68 will be with paired T-test. The CTC analysis will be presented in a descriptive way.

Sample Size Calculation

To calculate the sample size, we considered the disease control rate H0 at 6 months of 50 percent (placebo arm result of the phase III studies) 5,23 and H1 as a 6 months disease control rate of 70 percent. A 10 percent bitailed type I error was considered, 80 percent power loss and 30 percent follow up loss. With these calculations, the sample number will be 22 patients.

Recruitment and Study Duration

At the AC Camargo Cancer Center, 30 patients with advanced NET are treated annually. Therefore, considering the patients already under treatment and the possible candidates without previous treatment and that out of every 10 patients, N = 4 will meet eligibility criteria (NETs with positive HR), we estimate to recruit the study population in a maximum period of 3 years and have the first full evaluation in 3 ½ years.

Ethical Considerations

The study will be conducted in accordance with the protocol, Good Clinical Practice guidelines of the International Conference on Harmonization (ICH GCP) and applicable local laws and regulatory requirements. The Free and Informed Consent Term (ICF) must be in accordance with ICH GCP guidelines, local regulatory regulations, and legal requirements. See Appendix 2 for ICF.

The investigator should ensure that each study patient, or his / her legal representative, is fully informed about the nature and objectives of the study and

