Appendix

APPENDIX 1- RECIST 1.1

Subgroups that designated a response category (complete response [CR], partial response [PR], stable disease [SD] and progressive disease [PD], see definitions below) are all patients receiving at least one cycle of tamoxifen. All patients with an objective CR or PR response should have the response confirmed at least 4 weeks after the initial response documentation.

Radiological Response Rate

RECIST

The response and progression will be evaluated in this study using the new international criteria proposed by the RECIST (Response Criteria in Solid Tumors) committee.¹⁹ Changes only in the largest diameter (one-dimensional measurement) of tumor lesions are used in the RECIST criteria.

Measurable Disease. Measurable lesions are defined as those that can be accurately measured in at least one dimension (longer diameter to be recorded) as > 20 mm with conventional techniques (physical examination, CT, MRI) or as > 10 mm with spiral CT. All tumor measurements should be recorded in millimeters (or decimal fractions of centimeters).

The same evaluation method and the same technique should be used to characterize each lesion identified and reported in the baseline examination and during follow-up.

Clinical lesions: Clinical lesions will only be considered measurable when they are superficial (for example, cutaneous nodules, palpable lymph nodes). For the case of cutaneous lesions, the documentation is recommended by means of color photography, including a ruler to estimate the size of the lesion.

CT / MRI: Tomography and resonance are the best reproducible and currently available methods to measure target lesions selected for response assessment. Conventional CT and MRI should be performed with cuts of 10 mm or less in cross-section, contiguously. Spiral CT should be performed using a contiguous reconstruction algorithm of 5 mm. This applies to the chest and abdomen.

Unmeasurable disease. All other lesions (or disease sites), including small lesions (diameter greater than <20 mm with conventional techniques or <10 mm with spiral CT) are considered to be non-measurable diseases. Bone lesions, leptomeningeal disease, ascites, pleural / pericardial effusions, lymph nodes and cystic lesions are all non-measurable.

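### Scheduled imaging stops when a patient leaves for toxicity, so the 24-week primary outcome can be missing for patients whom the efficacy analysis includes

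*Combined protocol and SAP*

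**What the plan says.** - **Leaving for toxicity.** Table 3 suspends tamoxifen for grade 3 or higher, or intolerable grade 2, toxicity. If it has not improved within 3 weeks, or if 10 mg daily is not tolerated, "the patient will be excluded from the study for unacceptable toxicity".
- **Imaging.** Study design, item (2) Efficacy, schedules scans "every 12 weeks until progression or intolerance / exit from the study". Efficacy and Follow-Up Assessment repeats this: "every 12 weeks until progression or intolerance". Only patients with clinical but not radiological progression "may discontinue treatment with tamoxifen and continue imaging until progression". After exit for other reasons, the same section foresees imaging monitoring by the oncology team, with no week-24 date.
- **Primary outcome.** Disease control at 24 weeks, "defined by absence of radiological progression in conventional imaging" by RECIST 1.1.
- **Analysis set.** The Statistical plan specifies intention to treat: "Patients receiving at least one dose of tamoxifen will be evaluated for toxicity and efficacy".
- **Appendix 1.** The patients given a response category "are all patients receiving at least one cycle of tamoxifen". Administration sets a cycle at 42 days.
- **Missing outcomes.** The Sample Size Calculation allows for "30 percent follow up loss". No section says how a missing week-24 status is counted. The censoring rules concern progression-free survival only.

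**The concern.** The primary outcome needs a scan at a fixed time. The plan's own rules stop the scans for patients who leave for toxicity, while its analysis rule keeps those patients in. Where the week-24 status is missing, someone must decide how to count the patient, and without a written rule that can happen after the results are known. In a single-arm trial of 22 patients, leaving out toxicity stops, or carrying a stable week-12 scan forward to week 24, can make the disease control rate look too high. The one-cycle wording in Appendix 1 gives a textual ground for leaving out exactly the earliest toxicity exits.

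**Working it through.** **Inputs.** N = 22, null rate 50%, alternative 70%, two-sided type I error 10% (Sample Size Calculation); 42-day cycle (Administration); scans every 12 weeks (Table 1); 3-week recovery limit (Table 3). The plan gives no expected number of toxicity exits and names no test for the primary outcome. I assume an exact binomial test against 50% at upper-tail 0.05, half of the stated 10%.

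**The plan's figure of 22.** The usual formula gives n = [1.645 × √(0.5 × 0.5) + 0.842 × √(0.7 × 0.3)]² / 0.2² = 36.5, so 37, and 37/0.7 = 52.9, so 53 with 30% loss. The stated inputs do not reproduce 22. That is a separate matter; here 22 serves only as the denominator.

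**Step 1: two timelines.**
- *Early exit.* Suspended at the week 3 visit and excluded 3 weeks later, at week 6. The patient has taken about 21 days of tamoxifen, less than the 42-day cycle, and has not reached the first scheduled scan at week 12. The Statistical plan includes this patient; Appendix 1 gives no response category.
- *Later exit.* Stable at week 12, then stops for toxicity before week 24. No further scan is scheduled. The week-12 scan already meets the appendix's requirement for stable disease (documented once, more than 4 weeks from baseline), but the outcome is defined at 24 weeks.

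**Step 2: what the text favours.**
- *Early exit, never scanned.* Appendix 1 requires stable disease to be documented on imaging, so this patient does not qualify as controlled. The Statistical plan keeps the patient in the denominator. Together these point to not controlled. The competing reading is to leave the patient out under the one-cycle wording.
- *Later exit.* The text does not settle whether the week-12 result stands in for week 24.

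**Step 3: size.** Each patient is 1/22 = 4.5 percentage points. Suppose there is one exit and 15 of the other 21 are controlled. With P(X ≥ x) under Binomial(n, 0.5):

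| Exit counted as | Rate | p |
|---|---|---|
| Not controlled | 15/22 = 68.2% | 0.067 |
| Left out | 15/21 = 71.4% | 0.039 |
| Controlled (arguable only for the week-12 case) | 16/22 = 72.7% | 0.026 |

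The smallest significant counts are 16 of 22 and 15 of 21. With one exit, the rules therefore disagree only at exactly 15 of 21. The chance of that count is 18.8% if the true rate is 70% and 2.6% if it is 50%.

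With two exits, 20 patients remain. Left out and not controlled disagree only at 15 of 20 (15/20, p = 0.021; 15/22, p = 0.067). If both exits were stable at week 12 and counted as controlled, 14 of 20 is also affected (16/22, p = 0.026, against 14/22, p = 0.143). The chance of 14 or 15 of 20 is 37.1% at 70% and 5.2% at 50%. At other counts the conclusion does not change.

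**The case against.** The strongest reply is that the plan is less open than it looks, and much of that stands.

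- A reader might infer from the wording of the primary outcome that an unscanned patient counts as controlled. The documents do not support this: the outcome refers to RECIST 1.1 in Appendix 1, which requires stable disease to be documented.
- A reader might infer that the analyst may freely drop such patients. The intention-to-treat statement speaks against that. The one-cycle wording sits just above the heading on radiological response rate, so it may be meant mainly for the secondary response outcome. But response categories are also how progression and its absence are assigned, so the conflict remains.
- A reader might infer that any toxicity, related or not, triggers the Table 3 route. The safety section ties dose reduction to toxicity judged related to tamoxifen. Treatment suspension criteria lists adverse events as a reason to stop treatment, not to leave the study, so the Table 3 wording may be loose.
- Scans may exist. This is a single centre, post-exit imaging monitoring is foreseen, and Funding and Sponsorship of the Study treats conventional imaging as routine. This makes missing data less likely, but nothing requires a scan at week 24. Appendix 1's request to document progression after stopping treatment is in a note on clinical deterioration and has no schedule.
- Consent withdrawal and other loss leave the same gap in counting. That is right, and the counting rule should cover them. Toxicity is singled out because here stated rules end the scans.

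**Conclusion.** The point holds. Table 3 and the imaging schedule, followed as written, can leave the primary outcome missing for patients whom the analysis must include, and Appendix 1 conflicts with the Statistical plan on early exits. The main open cases are the patient stable at week 12 who stops before week 24, and the early exit dropped under the one-cycle wording.

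The number of such exits cannot be estimated from the documents. It is probably small, since the Tamoxifen section describes the serious effects as rare. The 30% allowance (0.30 × 22 = 6.6 patients) is for all follow-up loss and should not be read as a toxicity estimate. Nor do the documents show that the result will be biased: under the assumed test, a single exit matters only at 15 of 21. The change is worth making because each patient carries 4.5 points, there is no control arm, and the remedy is cheap.

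**What to change.** 1. In Table 3, replace exclusion from the study by discontinuation of tamoxifen.
2. In Study design, item (2), and in Efficacy and Follow-Up Assessment, continue the 12-weekly conventional imaging to at least week 24 after a stop for toxicity, unless progression comes first.
3. In Appendix 1, change one cycle to one dose, to match the Statistical plan.
4. As a supporting sentence in the Statistical plan, count any dosed patient without a week-24 assessment, for whatever reason, as not controlled.

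**Cost.** Four wording changes, plus two scans for a patient who stops before week 12, or one for a patient who stops between weeks 12 and 24. The disease control rate may be slightly lower, by 4.5 points for each patient counted as not controlled rather than controlled. Under change 2, a patient off tamoxifen with stable disease at week 24 counts as controlled, which may partly reflect slow natural growth. Report this openly, with a sensitivity analysis that counts every toxicity stop before week 24 as not controlled.

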Any	Any	Yes	PD	

* In exceptional circumstances, evident progression of non-target lesions may be accepted as evidence of disease progression.
 
Note:
 
Patients with significant clinical deterioration requiring discontinuation of treatment without objective evidence of disease progression should be described as "symptomatic deterioration - clinical progression". All efforts should be made to document objective progression even after discontinuation of treatment.

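### Censoring PFS at the last tamoxifen date when a clinically progressing patient starts new treatment conflicts with the PFS definition and probably biases PFS upward

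*Combined protocol and SAP*

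**What the plan says.** Four parts of the combined protocol and SAP bear on this point.

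- **Outcomes, Secondary (1)** runs PFS from day 1 of cycle 1 "to death from any cause or radiological progression by RECIST 1.1, whichever occurs first". Its one censoring sentence is: "Patients alive and without progression at the time of study analysis will be censored for time-to-event analysis". New treatment is not mentioned.
- **Efficacy and Follow-Up Assessment** adds a rule for one group: "Patients who present clinical progression at the investigator's judgment, but without radiological progression, may discontinue treatment with tamoxifen and continue imaging until progression". It then provides that "if new treatment is instituted, the last date of receipt of tamoxifen will be the date of censure in the analysis of progression-free survival". Scans are planned "at baseline and every 12 weeks until progression or intolerance". It also allows earlier scans: "Patients with suspected progression (eg worsening of symptoms) may perform images within less than 12 weeks to assess progression of disease".
- **Statistical plan** states: "Efficacy and toxicity analyzes will be performed by intention to treat". Time-to-event results are to be given as medians and Kaplan-Meier curves. No sensitivity analysis is planned for the censoring rule.
- **Appendix 1, closing note**, on patients who stop for clinical deterioration without objective progression: "All efforts should be made to document objective progression even after discontinuation of treatment".

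**The concern.** Kaplan-Meier estimation assumes that a censored patient has the same future risk as those who remain under observation. This rule censors only patients whom the investigator has just judged to be getting worse, so that assumption is unlikely to hold. If they carry a higher hazard than the patients still at risk, the curve and the median are too favourable. The trial has a single arm, so no control group shares the bias.

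The rule also sets aside outcomes that the Outcomes section counts. Two analysts could each follow the document and report different PFS results from the same data. The date is a lesser oddity: tamoxifen is taken daily and scans are 12 weeks apart, so the last dose is generally not a tumour assessment.

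**Working it through.** The plan gives no figure for PFS, so there is none to reproduce.

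**1. The two rules side by side**, for a patient with clinical progression, no radiological progression, who stops tamoxifen and starts new treatment:

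| Later course | Outcomes, Secondary (1) | Efficacy and Follow-Up Assessment |
|---|---|---|
| RECIST progression | event at progression | censored at last tamoxifen |
| Death | event at death | censored at last tamoxifen |
| Alive, progression-free at analysis | censored at analysis | censored at last tamoxifen |

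**2. Illustrative size.** The inputs are 12-weekly scans (from the plan) and a true 24-week PFS of 50%. The second is an assumption, set equal to the H0 disease control rate in Sample Size Calculation. Also assumed: a constant hazard, and a share f of true failures in each 12-week interval censored before the scan that would have shown progression. The documents give no value for f.

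The true proportion surviving each interval is s = √0.5 = 0.7071. Censored failures leave the risk set before the scan, so

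KM(24) = [ s / (s + (1 − f)(1 − s)) ]².

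- f = 0: 0.7071² = 50.0%
- f = 10%: (0.7071/0.9707)² = 53.1%
- f = 20%: (0.7071/0.9414)² = 56.4%
- f = 30%: (0.7071/0.9121)² = 60.1%

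A simulation of 20,000 patients gave 52.9%, 56.3% and 60.0%. In 22 patients, 50% PFS means 11 failures by week 24, so f of 10% to 30% is about 1 to 3 patients. If progression were seen the moment it occurred, the formula would be 0.5^(1−f), giving 53.6%, 57.4% and 61.6%. The median would be 24/(1−f), that is 26.7, 30.0 and 34.3 weeks instead of 24.

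**3. What the direction depends on.** Take 22 patients: 5 progress at week 12, 4 switch at week 18, 4 progress at week 24.

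- As written: (17/22)(9/13) = 53.5%.
- Switchers followed, none progressing by week 24: 13/22 = 59.1%.
- One progressing: 12/22 = 54.5%. Two: 11/22 = 50.0%. All four: 9/22 = 40.9%.

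Censoring implicitly lets 4 × 4/13 = 1.2 of the four fail. The estimate is too high once two or more do.

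**4. The date.** If the last clear scan was at week 12 and tamoxifen stopped at week 22, censoring at either date leaves the same risk set at week 24. In the simulation at f = 20%, both dates gave 56.3%. The effect can also be downward. Take 22 patients with 5 events at week 12, 4 at week 24, and the rest stable: KM is 13/22 = 59.1%. If one of the stable patients stopped tamoxifen at week 14 and later switched, the rule gives (17/22)(12/16) = 58.0%.

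**The case against.** The strongest reply is that the Efficacy section's rule is a specific provision supplementing a general one. The Outcomes section does not say that nobody else may be censored. That is fair as to drafting, and a reader who infers a flat prohibition goes too far. It does not settle what happens to progression or death after a switch: the event definition has no exception, and no order of precedence is stated.

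Second, the illustration assumes that every censored switcher has truly progressed, with a share that has no source. That stands. The rule covers clinical progression without radiological progression, and some of these patients may be stable on imaging. Eligibility also limits how often switching can be presumed, since patients generally have no established option or are candidates for watchful waiting, and disease needing cytotoxic or locoregional therapy is excluded.

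Third, there are safeguards. Early imaging on suspicion, and the Appendix 1 effort to document progression, can turn such cases into RECIST events if progression is found before new treatment begins. The early scan is optional, however, and the Efficacy section permits continued imaging after stopping without requiring it.

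Fourth, PFS is secondary, has no test or decision rule, and has no planned historical comparison; the historical rate serves the disease control endpoint. That limits the consequence.

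**Conclusion.** The point holds in this form: the two sections handle progression or death after a switch differently, the rule sits badly with intention to treat, and the censoring is probably informative, with upward bias. The direction rests on one assumption, that switched patients have a higher hazard than those still at risk. The size, about 53% to 60% against a true 50%, also rests on the assumed 10% to 30% share, a constant hazard, and true progression in every switched patient. It shows scale and is not a forecast.

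Three stronger readings are not supported:

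- That the censoring date itself inflates PFS. It has little numerical effect and can lower the estimate. Moving it to the last scan would neither cure nor reveal the bias.
- That the 40.9% in the 22-patient example is the true value. It holds only if all four switchers progress by week 24.
- That the primary endpoint is biased by this rule. Its wording is confined to PFS.

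The consequence is moderate.

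**What to change.** 1. Delete the censoring rule in Efficacy and Follow-Up Assessment. In the main PFS analysis apply the Outcomes definition: RECIST 1.1 progression or death from any cause, regardless of new treatment.
2. Add a sensitivity analysis that counts clinical progression followed by new anticancer treatment as an event at the date of clinical progression. Making this the main analysis is defensible, but it would put an investigator-judged event into an open-label trial and depart from the RECIST-only definition.
3. If a censoring analysis is also shown, censor at the last evaluable scan before the new treatment, not at the last dose, and do not present it as a check on the bias.
4. Report how many patients are affected.
5. Confirm that the dates of clinical progression and of new treatment are recorded. Neither the data list under Study design nor Table 1 names them.

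The cost is a wording change, one further analysis and possibly two added data fields. RECIST readings after a switch must also reach the trial database; the plan mentions imaging monitoring after study exit but sets no schedule for it. PFS may look less favourable, and progression or death after a switch may partly reflect the new treatment. None of this alters who may stop tamoxifen or receive other treatment.
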